10. MEASUREMENT OF EFFECT

As epigenetic agents may take many months to show their benefit as seen in MDS/AML studies, subjects receiving SGI-110 may continue receiving their assigned treatment if their disease progresses to leukemia or progression as discerned by the clinical investigator criteria if 1) the patient is clinically stable, 2) the patient is informed of their clinical results and agrees to continue therapy, and 3) the patient provider agrees that remaining on study would be appropriate for the patient.

10.1.1 Response Criteria: from Savona et al., An international consortium proposal of uniform response criteria for myelodysplastic/myeloproliferative neoplasms (MDS/MPN) in adults. *Blood*, 125(12):1857-65.

 • CR (presence of all of the following improvements)*

 • Bone marrow: $\leq 5\%$ myeloblasts (including monocytic blast equivalent in case of CMML) with normal maturation of all cell lines and return to normal cellularity*

 • Osteomyelofibrosis absent or equal to “mild reticulin fibrosis” (\leqgrade 1 fibrosis)†

 • Peripheral blood‡

 • WBC $\leq 10 \times 10^9$ cells/L

 • Hgb ≥ 11 g/dL

 • Platelets $\geq 100 \times 10^9/L$; $\leq 450 \times 10^9/L$

 • Neutrophils $\geq 1.0 \times 10^9/L$

 • Blasts 0%

 • Neutrophil precursors reduced to $\leq 2\%$

 • Monocytes $\leq 1 \times 10^9/L$

 • Extramedullary disease: Complete resolution of extramedullary disease present before therapy (eg, cutaneous disease, disease-related serous effusions), including palpable hepatosplenomegaly

 • Provisional category of CR with resolution of symptoms:‡ CR as described above, and complete resolution of disease-related symptoms as noted by the MPN-SAF TSS

 • Persistent low-level dysplasia is permitted given subjectivity of assignment of dysplasia*

 • Complete cytogenetic remission

 - Either a minimum 50% reduction in palpable splenomegaly of a spleen that is at least 10 cm at baseline or a spleen that is palpable at more than 5 cm at baseline becomes not palpable
- Symptom response
 - Improvement in symptoms as noted by decrease of $\geq 50\%$ as per the MPN-SAF TSS scoring <20 were not considered eligible for measuring clinical benefit.¶

↔* Presence of dysplastic changes, which may be interpreted within the scope of normal range of dysplastic changes, may still exist in the presence of CR as allowed in MDS IWG. Marrow should exhibit age-adjusted normocellularity in CR.

↔† If there is no significant fibrosis present on the initial bone marrow biopsy, a second biopsy is not required to prove resolution of fibrosis. Grading of fibrosis in measurement of treatment response should be according to the European Consensus System.67

↔‡ Given the current lack of a validated tool to assess complete resolution of symptoms in MDS/MPN, "CR with resolution of symptoms" (a complete resolution of disease-related symptoms as noted by the MPN-SAF TSS in presence of CR) will be a provisional category of disease response.

↔§ Loss of cytogenetic burden of disease by (via FISH or classic

karyotyping) known to adversely affect prognosis is required to reach complete cytogenetic remission. Decrease in the cytogenetic burden of disease must be by $\geq 50\%$ (via FISH or classic karyotyping) to be indicative of a partial cytogenetic response. Given variability of fluorescent probes used in FISH, cytogenetic normalization via FISH will depend on the performance characteristics of the specific probes used.

• Resolution of abnormal peripheral blood counts must persist for at least 2 separate analyses over at least 8 wk. In the case of proliferative MDS/MPN, CR will include resolution of thrombocytosis to a normal platelet count ($150-450 \times 10^9/L$) and resolution of leukocytosis to WBC $\leq 10 \times 10^9$ cells/L but $\geq 1.5 \times 10^9/L$. Hgb should be maintained > 11 g/dL and platelets $\geq 100 \times 10^9/L$ without the support of transfusions. Clinical benefit may occur when these changes occur in absence of other changes required for CR or marrow response. Platelet and packed red blood cell TI would be considered for clinical benefit, and duration of TI should be monitored. Reduction in myeloid precursors (promyelocytes, myelocytes, metamyelocytes, nucleated red blood cells) to less than appreciable levels ($\leq 2-3\%$) and/or $1 \times 10^9/L$ monocytosis in the absence of infection, cytokine treatment, or other reactive causes.

•	
• Table 3 Proposed criteria for measurement of disease progression in adult MDS/MPN
 
• Combination of 2 major criteria, 1 major and 2 minor criteria, or 3 minor criteria from list
 
• Major criteria
 
 • Increase in blast count* • <5% blasts: $\geq 50\%$ increase and to $>5\%$ blasts • 5-10% blasts: $\geq 50\%$ increase and to $>10\%$ blasts • 10-20% blasts: $\geq 50\%$ increase and to $>20\%$ blasts • 20-30% blasts: $\geq 50\%$ increase and to $>30\%$ blasts† • Evidence of cytogenetic evolution‡ • Appearance of a previously present or new cytogenetic abnormality in complete cytogenetic remission via FISH or classic karyotyping • Increase in cytogenetic burden of disease by $\geq 50\%$ in partial cytogenetic remission via FISH or classic karyotyping • New extramedullary disease • Worsening splenomegaly • Progressive splenomegaly that is defined by IWG-MRT: the appearance of a previously absent splenomegaly that is palpable at >5 cm below the left costal margin or a minimum 100% increase in palpable distance for baseline splenomegaly of 5-10 cm or a minimum 50% increase in palpable
---	---

CONFIDENTIAL

This document is confidential. Do not disclose or use except as authorized.

distance for baseline splenomegaly of >10 cm
• Extramedullary disease outside of the spleen
• To include new/worsening hepatomegaly, granulocytic sarcoma, skin lesions, etc.
• Minor criteria
• Transfusion dependence§

	Circle the one number that describes how, during the past 24 hours, fatigue has interfered with your	
	• General Activity	0 (Does not Interfere) 1 2 3 4 5 6 7 8 9 10 (Completely Interferes)
	• Mood	0 (Does not Interfere) 1 2 3 4 5 6 7 8 9 10 (Completely Interferes)
	• Walking ability	0 (Does not Interfere) 1 2 3 4 5 6 7 8 9 10 (Completely Interferes)
	• Normal Work (includes work both outside the home and daily chores)	0 (Does not Interfere) 1 2 3 4 5 6 7 8 9 10 (Completely Interferes)
	• Relations with other people	0 (Does not Interfere) 1 2 3 4 5 6 7 8 9 10 (Completely Interferes)
• Enjoyment of life	0 (Does not Interfere) 1 2 3 4 5 6 7 8 9 10 (Completely Interferes)	

CONFIDENTIAL

This document is confidential. Do not disclose or use except as authorized.

Splenomegaly and associated mechanical symptoms Other patient reported symptoms derived from an international patient survey	Filling up quickly when you eat (Early Satiety)	Examples	0 (Absent) 1 2 3 4 5 6 7 8 9 10 (Worst Imaginable)	
	Abdominal pain or discomfort	Examples	0 (Absent) 1 2 3 4 5 6 7 8 9 10 (Worst Imaginable)	
	Inactivity	Examples	0 (Absent) 1 2 3 4 5 6 7 8 9 10 (Worst Imaginable)	
	Cough	Examples	0 (Absent) 1 2 3 4 5 6 7 8 9 10 (Worst Imaginable)	
	Night Sweats	Examples	0 (Absent) 1 2 3 4 5 6 7 8 9 10 (Worst Imaginable)	
	Itching (pruritus)	Examples	0 (Absent) 1 2 3 4 5 6 7 8 9 10 (Worst Imaginable)	
	Bone Pain (diffuse not joint pain or arthritis)	Examples	0 (Absent) 1 2 3 4 5 6 7 8 9 10 (Worst Imaginable)	
	Documented fever at least once a week?	Yes or No If yes, state the actual temperature range: _____ C or F		
	Unintentional weight loss (i.e. not the result of planned weight loss such as diet +/- exercise) in the last 6 months in excess of 10 pounds?	Yes or No If yes, state how many pounds lost last 6 months: _____		
What is your Overall Quality of Life?	0 (As good as it can be) 1 2 3 4 5 6 7 8 9 10 (As Bad as it can be)			

CONFIDENTIAL

This document is confidential. Do not disclose or use except as authorized.

11. ADVERSE EVENT REPORTING REQUIREMENTS

11.1 Definitions

11.1.1 Adverse Event (AE)

An adverse event (AE) is any undesirable sign, symptom or medical condition or experience that develops or worsens in severity after starting the first dose of study treatment or any procedure specified in the protocol, even if the event is not considered to be related to the study.

Abnormal laboratory values or diagnostic test results constitute adverse events only if they induce clinical signs or symptoms or require treatment or further diagnostic tests.

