6.1 Anticipated Toxicities

6.1.1 Adverse Event List(s) for SGI-110

The most common AEs suspected by the investigators in Study SGI-110-01 to be related to the drug and observed to date in the MDS/AML population are: injection site pain, fatigue, nausea, thrombocytopenia, anemia and diarrhea. Based on the mechanism of action of the drug and its active form decitabine, myelosuppression (neutropenia, thrombocytopenia, and anemia) and the related consequences such as

CONFIDENTIAL

This document is confidential. Do not disclose or use except as authorized.

infection (e.g. pneumonia), sepsis, and bleeding are the most likely risks for the drug. Mucositis has also been reported.

Pain and burning at the injection site has been reported that are related to dose and volume of injection as well as the speed of injection. Care must be taken to avoid intradermal injection. Ice packs will be applied prior to injection of SGI-110 and the drug will be injected slowly, over 30-60 seconds. If the injection site events are reported at subsequent injections despite slow injection and the use of ice packs, pre-treatment with topical or systemic analgesics can be considered.

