6.2 Dose Modifications for adverse events

All adverse events should be reported and considered as part of the overall safety evaluation of SGI-110. The Investigator should try to the best of his/her ability to assess whether an adverse event is related or unrelated to SGI-110. Dose modifications are not required for hematologic toxicities, but may be considered at the investigator's discretion, in collaboration with the Sponsor. In general, SGI-110 should be held for any:

1. Grade ≥ 3 non-hematologic toxicity (except nausea/vomiting, diarrhea) that fails to resolve to < grade 2 within 72 hours despite appropriate management.
2. Persistent grade ≥ 3 neutropenia or thrombocytopenia beyond day 56 of cycle 1 in the setting of a hypocellular bone marrow biopsy and absence of residual disease
3. Other clinically significant adverse event which, in the opinion of the Safety Review Committee (SRC), would place subjects at undue safety risk.

After resolution of toxicity, treatment with SGI-110 may be resumed at dose level of 45 mg/m². Retreatment at the original dose level may be considered, depending on the nature of the AE, and after discussion with the principal investigator. If the same toxicity that led to the dose reduction occurs again at this dose level, SGI 110 can be resumed at 30mg/m² after the toxicity has resolved to Grade ≤ 2 or baseline levels. Missed doses will be replaced at the investigator's discretion. Dose modifications for drug-related hematological toxicities will be managed on a case-by-case basis, depending on the patient's disease status and response to growth factor support, in collaboration with the principal investigator. There is no mandatory dose reduction or delay for hematological toxicity, but delays up to 14 days and dose reductions down to 30 mg/m² will be permitted depending on clinical circumstances, after discussion with the principal investigator. Additional delays or dose reductions may be considered after discussion with the principal investigator at Weill Cornell Medical Center.

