may be required in order to observe clinical benefit with the proposed treatment, there will be no assessment of efficacy until at least 25 patients have been treated for at least 4 cycles of therapy. If, at that point, there are fewer than 10% responses, as defined in the protocol, the study will be stopped for futility. The WCMC DSMB may also convene as needed if stopping criteria are met or other safety issues arise that the Principal Investigator and/or IRB would like the WCMC DSMB to address.

Stopping criteria also include:

- The early death of more than three of the first ten subjects, as defined by death within 28 days of beginning therapy.
- If there is an unacceptable rate of Grade 4 toxicities, as judged by the investigation team, study sponsor, or the WCMC DSMB.

The study PI will submit all written DSMB recommendations to the IRB upon receipt.

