The primary endpoint of the hematological response proportion will be calculated and a 95% confidence interval will be estimated via binomial proportions. Descriptive statistics will be utilized to describe the parameter proportion defined above (i.e., frequency, percent). Estimated differences in the hematological response proportion between categories of demographic and treatment variables of interest (evaluated by the two-sample t-test, Wilcoxon rank-sum test, Fisher's exact test, and chi-square test, as appropriate) will serve as preliminary data (i.e., hypothesis-generating) for future studies. Similar analyses will be conducted for secondary outcomes of quality of life. Exploratory analyses of the hematological response rate and quality of life outcomes will be also be stratified by specific cytogenetic and/or molecular subgroups of MPN.

All p-values will be one-sided with statistical significance evaluated at the 0.05 alpha level. One-sided ninety-five percent confidence intervals will be calculated to assess the precision of the obtained estimates. All analyses will be performed in SAS Version 9.3 (SAS Institute, Inc., Cary, NC) and Stata Version 13.0 (StataCorp, College Station, TX).

Safety Analyses:

The frequency of subjects experiencing toxicities will be tabulated. Toxicities will be assessed and graded according to CTCAE v. 4.0 terminology. Exact 95% confidence intervals around the toxicity proportions will be calculated to assess the precision of the obtained estimates.

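### Asymptomatic grade 3-4 cytopenias that lead to no treatment or further test can be left out of the safety table, because no direct grading of laboratory values is planned

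*Combined protocol and SAP*

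**What the plan says.** Under Section 11.1.1, abnormal laboratory values "constitute adverse events only if they induce clinical signs or symptoms or require treatment or further diagnostic tests". Severity is not a criterion, and hematology values are not treated separately.

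Section 6.1.1 names "myelosuppression (neutropenia, thrombocytopenia, and anemia) and the related consequences such as" infection, and closes the sentence with "sepsis, and bleeding are the most likely risks for the drug".

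Section 11.2 has adverse events and serious adverse events, including those found by laboratory test, entered in the medical record and on case report forms. Section 11.4.2 puts the non-serious ones on the toxicity form.

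The analysis text is short. Safety Analyses in Section 14.1 opens with "The frequency of subjects experiencing toxicities will be tabulated". It then names CTCAE version 4.0 as the grading scale and asks for an exact 95% interval around each toxicity proportion. Section 5.1 adds a descriptive tabulation by organ system. Neither section mentions a laboratory table.

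Section 12.1 gives as one stopping criterion "If there is an unacceptable rate of Grade 4 toxicities", which is left to judgement without a numeric limit.

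**The concern.** The toxicity expected most from this drug is one that is found on a blood count. The adverse-event definition filters blood counts by what follows from them, not by how severe they are. If the safety table is built from recorded adverse events, a grade 4 neutrophil count in a patient who feels well, receives nothing for it and has no additional test is not counted.

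Two things are at stake. First, the reported rate of severe cytopenia could be too low, and how far would depend on how readily each physician treats or retests. Practice could also differ between sites if the study opens to others, as Section 1.1 allows. Second, those who judge the Grade 4 rate may be working from an incomplete count. The protocol plans no other tally: a footnote to the progression criteria in Section 10 keeps treatment-caused cytopenias out of the progression assessment, so the safety table is the only planned place to count them.

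**Working it through.** The plan gives no figure on this point, so there is none to reproduce. The check follows the definition through to the analysis and then illustrates the possible size.

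**Step 1: the route from blood count to table.**
- Definition (11.1.1): a value qualifies by symptoms, treatment or additional testing. Grade plays no part.
- Recording (11.2, 11.4.2): a laboratory finding reaches the forms as an adverse event. No second route for graded laboratory values is named.
- Analysis (5.1, 14.1): toxicities are tabulated. No worst-grade, shift or nadir summary of blood counts is planned.
- Review (12.1): the Grade 4 rate is judged. The data source for that rate is not stated.

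**Step 2: do other clauses bring the missing counts back?**
- The definition of a serious adverse event (11.1.2) cites blood dyscrasias as an example, but an event must be an adverse event before it can be serious.
- The Grade 4 reporting rule (11.4.1) sits under serious adverse event reporting and speaks of events. It does not say that a laboratory value excluded by 11.1.1 counts as one.
- Supportive care (5.4 and its subsections) permits antibiotics, growth factor and red-cell transfusion. Each use for a low count would make that count an adverse event, but the use is permitted or discretionary, not required by grade.

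The group that can be lost is therefore narrow: no symptoms, no treatment and no further test.

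**Step 3: illustration of size.** Inputs: n = 50 (planned enrolment, 14.1) and n = 15 (first DSMB safety review, 12.1). The true rate p and the recorded share c are assumptions. Tabulated count x = n × p × c, rounded to a whole patient. The exact (Clopper-Pearson) interval, taken as two-sided, has lower limit Beta⁻¹(0.025; x, n − x + 1) and upper limit Beta⁻¹(0.975; x + 1, n − x).

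| n | True rate (assumed) | Share recorded (assumed) | Tabulated | Exact 95% CI | Contains true rate? |
|---|---|---|---|---|---|
| 50 | 50% | 100% | 25/50 = 50% | 35.5-64.5% | yes |
| 50 | 50% | 80% | 20/50 = 40% | 26.4-54.8% | yes |
| 50 | 50% | 60% | 15/50 = 30% | 17.9-44.6% | no |
| 50 | 40% | 75% | 15/50 = 30% | 17.9-44.6% | yes |
| 50 | 40% | 50% | 10/50 = 20% | 10.0-33.7% | no |
| 15 | 60% | 100% | 9/15 = 60% | 32.3-83.7% | yes |
| 15 | 60% | 75% | 7/15 = 46.7% | 21.3-73.4% | yes |
| 15 | 60% | 50% | 4/15 = 26.7% | 7.8-55.1% | no |

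In the two n = 15 rows with partial recording, x was rounded from 6.75 and 4.5. The direction is always downward, because true cases are omitted. Whether the interval still covers the true rate depends entirely on the assumed share.

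**The case against.** The strongest reply is that the analysis sections speak of toxicity, not adverse events. Sections 5.1, 6 and 14.1 tie toxicity to CTCAE version 4, and Section 6.2 uses the word for states defined by laboratory grade, such as persistent neutropenia of grade 3 or higher. A programmer could read this as an instruction to grade every blood count, and Section 11.4.2 does not say that the toxicity form excludes other graded values. This stands as a permissible reading. Nothing requires it, however, and the one route that is spelled out goes through adverse events. An ambiguity about the main expected toxicity is better settled in writing.

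Four stronger readings are tempting, and the documents do not support them.

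- *That severe cytopenias as a class will be missed.* Many will meet the definition through transfusion, growth factor, antibiotics or an extra test.
- *That Section 6.2 shows severe cytopenias go without action.* It says "Dose modifications are not required for hematologic toxicities", but dose change is not part of the test in 11.1.1. The sentence says nothing about whether treatment or testing follows.
- *That the DSMB will judge on an incomplete count.* After its first review it sees cumulative study data twice a year, and the investigation team or sponsor may also judge the Grade 4 rate. None of them is said to be limited to adverse-event forms. With no numeric limit, no particular decision can be shown to change.
- *That the exact intervals would be wrong.* They are valid for the proportion as recorded. The difficulty is that this proportion may not be the rate of severe cytopenia.

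One further objection stands and shapes the remedy. Section 2.4 describes anemia that generally needs transfusion, and sometimes leukopenia or thrombocytopenia, as part of the disease. A worst-grade table alone would mix disease with drug effect.

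**Conclusion.** The concern holds in a limited form. As written, the plan allows asymptomatic grade 3-4 cytopenias that prompt no treatment or further test to be left out of the safety table, and possibly out of the Grade 4 review. Rates of a main expected toxicity may therefore be understated.

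The amount cannot be estimated from the documents. The illustrations run from a 10-point shortfall, with intervals that still cover the true rate, to 20 points or more, with intervals that do not. They rest wholly on assumed rates and capture shares. The conclusion also assumes that the safety table follows the named adverse-event route. If the sponsor already intends to grade every count directly, only a sentence saying so and the baseline comparison are missing.

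The primary response analysis is not affected. This is a worthwhile clarification of the safety analysis, not a flaw in the design.

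**What to change.** Leave the adverse-event definition in 11.1.1 as it is. Add to Safety Analyses in 14.1 a statement that hematology and chemistry results already collected will be graded by CTCAE v4.0 from the values themselves, whether or not symptoms or action followed. The table should show each patient's worst post-baseline grade together with the shift from baseline grade. State in 12.1 that the DSMB receives it alongside the adverse-event table when it considers the Grade 4 rate.

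The cost is one programmed table with no new visit or sample, provided that the values themselves, baseline included, are held in the study data; Section 13.6 leaves the collection system open.

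There are two drawbacks. Reported cytopenia rates will be higher and will partly reflect the underlying disease, so they must be read against baseline grade. In addition, the study calendar in Section 9, as it reads in the text available for this review, shows no blood count at Course 1 Day 14. The sponsor should check this against the laid-out table. If it is correct, the new table will capture first-cycle cytopenias only in part, and the 15-patient safety review relies on that period.

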11.1.2 Serious adverse event (SAE)

A serious adverse event (SAE) is any adverse event, occurring at any dose and regardless of causality that:

- Results in death
- Is life-threatening. Life-threatening means that the person was at immediate risk of death from the reaction as it occurred, i.e., it does not include a reaction which hypothetically might have caused death had it occurred in a more severe form.
- Requires or prolongs inpatient hospitalization (i.e., the event required at least a 24-hour hospitalization or prolonged a hospitalization beyond the expected length of stay). Hospitalization admissions and/or surgical operations scheduled to occur during the study period, but planned prior to study entry are not considered SAEs if the illness or disease existed before the person was enrolled in the trial, provided that it did not deteriorate in an unexpected manner during the trial (e.g., surgery performed earlier than planned).
- Results in persistent or significant disability/incapacity. Disability is defined as a substantial disruption of a person's ability to conduct normal life functions.
- Is a congenital anomaly or birth defect; or
- Is an important medical event when, based upon appropriate medical judgment, it may jeopardize the participant and require medical or surgical intervention to prevent one of the outcomes listed above. Examples of such medical events include allergic bronchospasm requiring intensive treatment in an emergency room or at home; blood dyscrasias or convulsions that do not result in inpatient hospitalization, or the development of drug dependency or drug abuse.

Events **not** considered to be serious adverse events are hospitalizations for:

CONFIDENTIAL

This document is confidential. Do not disclose or use except as authorized.

- routine treatment or monitoring of the studied indication, not associated with any deterioration in condition, or for elective procedures
- elective or pre-planned treatment for a pre-existing condition that did not worsen
- emergency outpatient treatment for an event not fulfilling the serious criteria outlined above and not resulting in inpatient admission
- respite care

